#### **4.3. Inclusion and Exclusion Criteria**

Eligible children will be identified during a screening at initial presentation. They must fulfill the inclusion criteria which include (Appendix 10, CRF 10):

- Patients must be ages 2-10.
- Presence of at least one active (soft) cavitated carious lesions in the primary dentition, extending into dentin (ICDAS 5 or 6) – Only one tooth will be selected for the study. All others will be restored and monitored according to the American Academy of Pediatric Dentistry (AAPD) guidelines.
- The selected tooth must have a one or two surface lesion (more than 1/3 of the crown of the tooth must be remaining) and must allow for direct application of SDF.
- Study teeth will not have any spontaneous or elicited pain due to caries, tooth mobility, or signs of pulpal infection.
- Selected primary teeth must have an anticipated exfoliation date greater than 12 months away.

Exclusion criteria include children with:

- Hereditary developmental defects such as Amelogenesis Imperfecta and Dentinogenesis Imperfecta
- Severe medical conditions that do not allow the child to be managed in the MCHC/UMSOD clinics
- Known allergy /sensitivity to dental materials being used, including SDF

- Inability of the child to cooperate for treatment, recall examinations, or periapical radiographs.
- Wards of the State, for consenting reasons

After approaching the parent with a brief discussion of the study, determining interest and asking brief pre-screening eligibility questions as approved by the Institutional Review Board (IRB), the informed consent process will occur. Parents will provide both written and verbal consent, and written and verbal assent will also be asked of the children older than age 8 (Appendices 2 &3). Following the informed consent process, full study eligibility criteria will be reviewed with the pediatric dental resident performing the procedure. At time of consent, the parent will also be provided the *Enrollment Information Form* (Appendix 4) as a reminder of important information and frequently asked questions. This form will include information regarding study purpose, duration (12 months, including application/restorative appointment, 3 follow-up visits, and additional follow-up phone calls/contacts), possible resulting appearance, and overall study protocol.

Children who are enrolled to participate in the study will receive a full mouth caries examination using the ICDAS criteria (Examiners will be trained and calibrated in the ICDAS criteria prior to study initiation.), and will be randomly divided into two groups:

1. **Conventional management of caries group:** This group will receive traditional restorative care for one tooth with a one or two surface lesion – including composite, amalgam, or glass-ionomer restorations according to the current AAPD treatment guidelines.
2. **SDF management of caries group:** This group will receive applications of SDF applied to their carious lesion, in lieu of restoration placement, with the goal of “arresting caries”.

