## **2. Objectives**

The objectives of this clinical study are to evaluate:

- The effectiveness of treatment of cavitated caries in children by application of silver diamine fluoride (SDF) in comparison to conventional restorative treatments
- The perceptions of parents and patients to both treatment modalities and their levels of acceptability
- The opinions of dental providers in terms of ease of use and clinical time spent
- The relative cost-effectiveness of the two treatment approaches regarding both practitioner chair time and material-based cost

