### **4.2. General Outline**

Children, 2-10 years of age will be invited to participate. The original study site is Mott Children's Health Center (MCHC) in Genesee County, Michigan. Following a slow recruitment period, the University of Michigan School of Dentistry (UMSOD) Children's Clinic was added as a second study site. Given the current data in the literature, the combined failure rate for conventional restorative techniques (e.g. compomers) is approximately 29% at one year follow-up, while application of silver diamine fluoride has a failure rate of 63% at one year follow-up, with increased success over time. Although the failure rate of SDF at one-year follow-up seems alarming, as indicated by Zhi, *et al.* it may be possible to increase the success rate with additional applications providing success rates up to 90.1% at 24 months. Using these data,  $\alpha$ -value of 0.05 and a Power set at 80%, the resulting sample size would be 68 (34 per group) as calculated using the software, nQuery (Appendix 1). To account for 30% attrition, the final number needed for the initial study will be 98 (92 for 25% attrition, 86 for 20% attrition). Subjects will be contacted by phone regularly and invited to two intermediate clinic visits (plus a final study visit) to reduce attrition (Table 1). Given a review of the current literature of the few Randomized Controlled Clinical Trials involving SDF worldwide, the majority of this research has been completed with pre-school aged children. Almost all research discusses arresting or prevention of caries in the

primary dentition, as well as prevention of caries on first permanent molars. Due to the strength of the current research, this study will be focused on the primary dentition of children in the U.S. These children and their parents will be approached when presenting for examination/recall/or treatment at Mott Children's Health Center, Flint, MI, or the University of Michigan School of Dentistry Children's Clinic, Ann Arbor, MI. Interested families with children that qualify following screening examination will be provided with an *Informed Consent/Assent* (Appendix 3) and an *Enrollment Information Form* (Appendix 4).

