## **9. Withdrawal Procedures**

Subjects will have the right to withdraw at any time. Alternative conventional treatment can also be provided to the SDF group at any time, if it is believed by the provider to be in the patient's best interest. Reasoning will be recorded, as a preference for or against one treatment arm may provide further information as to public acceptance of a treatment, and these subjects will be withdrawn, *CRF 04 Treatment Deviation* (Appendix 10, CRF 04) and appropriate additional forms will be completed and the parent will receive a *Study Completion or Disenrollment Letter* (Appendix 11). Although no adverse events are expected *CRF 15 Unanticipated Problem & CRF 16 Adverse Event Logs* will be available if necessary (Appendix 10, CRF 15 & 16). In the event that the protocol is ever deviated from (ie. Missed recall or appropriate study procedure not completed) a *CRF 14 Protocol Deviation* (Appendix 10, CRF 14) will be completed.

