## **10. Statistical Analysis**

Power of the study will be fixed at 80% ( $\beta=0.20$ ) just as was used in calculation for necessary sample size, with  $\alpha = 0.05$  as the significance level. Data will be entered into SPSS Statistics or

another secured data collection system and data will be analyzed. Information will be stored on a password protected computer using an encrypted file and will be maintained as confidential protected health information (PHI). Examiners will be trained at the start of the study and calibrated on the use of the ICDAS criteria, and on the clinical outcome variables using extracted teeth to determine intra and inter-examiner reliability (dentin color, dentin hardness, and lesion size in mm), which will be measured with kappa statistics. A Chi-square test will be applied to determine if there is a difference in distribution of variables such as age, gender, brushing habits, fluoride exposure, etc. Chi-square tests will also be used to determine differences in dropout rates, failure rates, patient satisfaction/acceptance, and overall cost. The primary outcome, the proportion of children reporting major failures during the 12 month follow up period, will be analyzed using a mixed model with a binomial error structure. We will also analyze minor failures in a similar manner. The dependent variables will be a binary indicator of major failure, with differences between study treatments fitted as fixed effects. Estimates of the relative risk of major failure in the two groups will be presented in the form of odds ratios and associated 95% confidence intervals. Within this framework we will be able to estimate:

1. The mean difference between groups at the end of the follow up period;
2. The mean difference between groups across the whole of the follow up period; and
3. The difference in the rate of change of the outcome across the follow up period

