## **11. Potential Limitations**

An initial potential problem in the study may be to obtain the 98 patients needed per the power analysis calculation. Hopefully this will not remain too much of an obstacle, as children are frequently seen at Mott Children's Health Center and University of Michigan School of Dentistry Children's Clinic with carious lesions of this nature. When enrolling in this study, parents are either simply enrolling their children in a study where they would be provided the care that they would otherwise be provided outside of the study or, if receiving the alternative SDF treatment, they always have the ability to opt out and receive their definitive, conventional treatment. At the completion of the study, children who received care in the SDF group will have their study teeth restored according to AAPD guidelines or monitored for exfoliation, whichever is deemed most appropriate by their final provider or elected by the parent.

In order to prevent confusion and withdrawal from the study following intervention due to misinformation, all residents at Mott Children's Health Center and the University of Michigan School of Dentistry Children's Clinic who are providers for this study will be standardized in terms of the presentation of the study to the parents and patients and in the informed consent and assent process for the parents and children involved. It is important that these patients and their parents understand especially how the tooth may look following treatment. Teeth treated with SDF may become darker, and it is important to standardize this presentation by all residents so that patients are not withdrawing from the study simply because they were unaware of these anticipated consequences of the treatment.

In order to achieve a sample population of this size in such a short amount of time, five or six residents at each clinical site will be completing the screening, treatment, and recall of these patients. While having many providers is a limitation of the study, all providers will be trained and calibrated in their assessment of the tooth color and hardness as well as in their SDF application technique.

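### Acceptability is rated only by families who consent and stay: no count of refusals is described, and withdrawals over dislike have no stated place in the acceptance test

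*Combined protocol and SAP*

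**What the plan says.** Section 2 lists among the objectives "The perceptions of parents and patients to both treatment modalities and their levels of acceptability".

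On recruitment, Section 4.2 says: "These children and their parents will be approached when presenting for examination/recall/or treatment at Mott Children's Health Center", or at the second clinic. Section 4.3 then gives the order: "After approaching the parent with a brief discussion of the study, determining interest and asking brief pre-screening eligibility questions", followed by consent, with randomisation after enrolment. The information form handed over at consent covers "possible resulting appearance, and overall study protocol". Section 11 standardises what residents say about darkening of the tooth, so that "patients are not withdrawing from the study simply because they were unaware of these anticipated consequences of the treatment".

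Section 7.1 has parents and children complete questionnaires at the 3-, 6- and 12-month recalls and at emergency visits. There are baseline questionnaires too, but Table 1 first lists parent satisfaction at the 3-month visit.

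Reasons for withdrawal after enrolment are recorded (Sections 4.4 and 9, CRF 04). Section 9 explains why: "as a preference for or against one treatment arm may provide further information as to public acceptance of a treatment". Section 10 plans the analysis in one sentence: "Chi-square tests will also be used to determine differences in dropout rates, failure rates, patient satisfaction/acceptance, and overall cost".

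**The concern.** Section 3.4 names the black stain as the most notable drawback of SDF. A family that objects to it can leave at two points: by declining when approached, or by withdrawing after treatment. The plan itself treats rejection of an arm as evidence about acceptance, yet neither exit has a defined place in the acceptance analysis.

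The two exits have different consequences. Refusal before randomisation limits the families to whom the result applies. Withdrawal after randomisation can also distort the comparison between arms, because SDF families may move to conventional treatment at any time and are then withdrawn (Sections 9 and 11). Such a family may give no later rating, so the clearest non-acceptors could drop out of the test. The report might then show similar acceptance in the two arms and be read as a statement about families in general.

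**Working it through.** **Step 1. Follow each type of family through the plan.**

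| Family | What the supplied text records | Enters the acceptance test? |
|---|---|---|
| Approached, declines | Nothing described | No |
| Enrolled, stays | Questionnaires at recall and emergency visits (Section 7.1) | Yes |
| Enrolled, withdraws over the treatment | Reason for withdrawal (Sections 4.4 and 9) | Not stated (Section 10) |

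The plan gives no figure for acceptability that could be reproduced: no number approached, no refusal rate, no expected acceptance. Steps 2 and 3 are illustrations, and their inputs are assumptions unless a source is named.

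**Step 2. Refusals at approach.** Let *a* be acceptance of SDF among enrolled families, *r* the share of approached eligible families who decline, and *s* the share of those refusals that are due to SDF or staining. Suppose that families declining for other reasons would have accepted at rate *a*. Then hypothetical acceptance among all approached is *a*(1 − *rs*). With *a* = 90%:

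| *r* | *s* = 0 | *s* = 0.5 | *s* = 1 |
|---|---|---|---|
| 10% | 90% | 85.5% | 81% |
| 30% | 90% | 76.5% | 63% |
| 50% | 90% | 67.5% | 45% |

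For example, 0.90 × (1 − 0.30 × 0.5) = 0.765. Over this grid the overstatement runs from 0 to 90 − 45 = 45 points. It is zero whenever refusals have nothing to do with SDF.

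**Step 3. Withdrawals over dislike.** Let *w* be the share of an arm that withdraws for dislike without having given a rating, with no other losses, and let *a* be acceptance among those who do rate, equal in both arms. The questionnaire-only difference between arms is *a* − *a* = 0. Counting these withdrawals as not acceptable gives *a*(1 − *w*) in each arm and a difference (SDF minus conventional) of −*a*(*w*_SDF − *w*_conv). With *a* = 90% and *w*_conv = 0:

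- *w*_SDF = 0: difference 0.
- *w*_SDF = 10%: 0.90 × 0.90 = 81%, difference −9 points.
- *w*_SDF = 30%: 0.90 × 0.70 = 63%, difference −27 points.

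The 30% case uses up the whole attrition allowance of Section 4.2 (34/0.70 = 48.6, so 49 per arm and 98 in all) and is an extreme. If dislike withdrawals are equally common in both arms, the difference stays at 0.

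**The case against.** Consent is not a commitment to SDF. Allocation is 1:1, SDF families may opt out to conventional treatment at any time, and participation pays up to $300. A reluctant family can therefore enrol, reject SDF and have its reason recorded, and dropout is itself compared by chi-square. This stands, and it means that the sample cannot be described as having already accepted the stain. It does not settle how those rejections count in the acceptance test; a separate dropout comparison, which pools all reasons, does not do so.

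The direction of selection is also open to argument. Families averse to injection, rubber dam and drilling (Section 5.1) may decline too, and others may decline because of visits or research in general. Section 3.4 reports earlier work in which discoloration did not reduce satisfaction. Against this, Section 11 says that conventional care is what families would receive outside the trial, so declining avoids SDF but not a restoration. That makes overstatement plausible without showing it.

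The case report forms and appendices are not in the supplied text, and a screening log may be among them. A reader might infer that refusals go unrecorded; the most that can be said is that no recording is described and that Section 10 makes no use of one.

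Finally, any trial that needs consent has this limit on generalisation, and acceptability is not the primary outcome. Both points are right, and they keep the matter at the level of a worthwhile, inexpensive change.

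**Conclusion.** The point holds in a limited form. Acceptability is measured in families who consented after disclosure of the possible appearance and who remain to be asked. No count of refusals is described, and the handling of preference-driven withdrawals in the acceptance test is unstated. Acceptance of SDF may be overstated for eligible families in general.

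A reader might go further and conclude that acceptance is overstated, or overstated by a given number of points. The documents do not support that: every input in Steps 2 and 3 except the 30% attrition allowance is assumed, and both ranges include zero. Nor does refusal before randomisation bias the between-arm comparison among consenters. The threat to that comparison comes from omitting withdrawals over dislike, and only if their frequency differs between arms.

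The primary outcome and the sample size are unaffected.

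**What to change.** 1. In Section 10, count a withdrawal whose reason on CRF 04 is dislike of the assigned treatment or its appearance as not acceptable in the acceptance analysis, by the same rule in both arms. Show the questionnaire-only result as a sensitivity analysis. Withdrawal for another recorded reason is not covered by this rule.
2. From now on, as the IRB permits, keep an anonymous tally of families approached, eligible and declining, with one voluntary reason code. Report it descriptively in the participant flow. Do not merge it into an acceptance rate for all approached families: declining a trial is not rating a treatment, and each randomised family rates only the treatment it received.
3. Word the acceptability conclusion as applying to consenting families.

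Cost: item 1 takes a few sentences and uses a reason already collected. Item 2 takes one line per approach and probably a minor IRB amendment. Some reasons will be unknown. Section 4.2 shows that recruitment had begun before the second site was added, so families approached earlier may not be countable. Reported SDF acceptance may turn out less favourable. If the tally is not feasible, items 1 and 3 can still be adopted.

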#### **4.4. Participant Allocation and Blinding**

Subjects enrolled in the study will be randomly assigned to one of the two caries management groups in a 1:1 ratio. Although treatment will be randomly assigned, it will not be possible to blind parents, children, or dentists to the assigned treatment group as the post-operative appearance is likely to differ markedly between groups. In the event treatment for the patient is failing, regardless of the treatment arm assigned, the provider will recommend additional treatment and can withdraw the patient at any time and appropriate reasoning will be recorded. Patients/parents have the right to withdraw from the study at any time and for any reason as well. Additionally their reasoning for withdrawal will be recorded (Appendix 10, CRF 04, 11, 14-17).

## **5. Interventions**

Patients will be randomly assigned to the following groups, and managed under that philosophy for a 12 month period. Each appointment for either intervention group will follow the designated *Workflow* for that appointment (Appendix 5-8) and appropriate subsequent documents will be completed at each visit (Appendix 9).

### **5.1. Conventional management of caries**

These children will receive restorative dental care in alignment with the AAPD guidelines, within the confines of the MCHC or UMSOD clinics. This treatment typically includes administration of local anesthesia, placement of rubber dam, caries removal with rotary and hand instruments, and placement of a final restoration. Following completion of the conventional caries management, the provider will complete the *CRF 02 Intervention Visit: Conventional Restoration CRF* (Appendix 10, CRF 02). For both study interventions, fluoride varnish application should not be applied within one week before or after study intervention so that the effects noted will not be confused with known positive effects of topical fluoride varnish applications.

### **5.2. SDF management of caries**

- The selected tooth with notable decay into dentin will be isolated with cotton rolls.
- No caries removal will be performed, except for food or other obvious debris.
- Tooth will be dried with gauze and SDF solution will be placed on the carious dentin until it is saturated.
- Excess SDF will be blotted dry with a cotton pellet.
- A second application of SDF solution will then be placed to ensure that the entire carious surface is wetted, and excess will again be blotted with a cotton pellet.
- Following the second application of SDF, the area will be isolated for 3 minutes to allow for ample drying before allowing contact with saliva and soft tissues
- Should the SDF come in contact with any soft tissues, soft tissue should immediately be wiped with a saline wipe
- Following completion of the SDF intervention visit, the provider will complete the CRF 03 *Intervention Visit: Silver Diamine Fluoride* CRF (Appendix 10, CRF 03).
- A second application of SDF will be applied at 6 month recall, following the same protocol as noted above (Due to the potential for increased caries arrest rate with a 6 month application).
- Any new carious lesions that develop after the initial treatment will be recorded, and treated using conventional treatment methods and will not be included in the study.
- Following the completion of this study, teeth in the SDF group will be treated according to AAPD guidelines or observed for exfoliation. The parent of an SDF treated child can elect a restoration following AAPD guidelines at the 12 month visit.

Both groups will receive the following, according the standard procedures at the MCHC/UMSOD:

- Oral Health Instruction (OHI) and diet instruction
- Tooth brushing/dentifrice use at home
- Fissure sealants for permanent teeth will be placed if deemed necessary.
- Traditional preventative care at recalls based on AAPD guidelines (Regular recall exams, prophylaxis, scaling, flossing, and fluoride varnish at 6 month recalls will be provided for both treatment arms. Special care will be taken to not apply fluoride varnish directly to the carious lesion which is being treated with SDF.)

## 6. Study Visits and Intermediate Contacts

Recalls for both groups will occur via phone questionnaire as well as follow-up visits. Participants will be contacted at 1 month, 2 months, 4.5 months and 9 months ( $\pm$  2 weeks) following restoration placement or application of SDF. Subjects will need to present to the clinic for follow-up visits at 3 months ( $\pm$  6 weeks), 6 months ( $\pm$  6 weeks), and for study completion at 12 months ( $\pm$  6 weeks) (Table 1). Subjects will also be called to schedule and confirm these follow-up visits; these short calls will require no payment to the study subjects. In the case of an emergency, an emergency visit will be scheduled at Mott Children's Health Center or the University of Michigan School of Dentistry. An emergency will be evaluated and treated according to the AAPD guidelines, followed by completion of appropriate case report forms (CRFs) and reporting to IRBs and study sponsors (Appendix 10, CRF 14-17). In the event of minor or major failure in either study group, the subject will be withdrawn from the study and teeth will be given the appropriate treatment as stated in the AAPD Guidelines free of charge, these teeth will be categorized as a failure, and a *CRF 04 Treatment Deviation CRF (Appendix 10, CRF 04)* will be completed.

**Table 1.** Patient Contact Interval

Patient Contact	Recall Interaction	Time Scale
Clinic Visit #1	Consent/Accent, baseline questionnaires, initial caries assessment, radiographs*, intervention	T = 0
Intermediate Contact	Attrition prevention, update contact information, follow-up on pain	T = 1 month, 2 months (Additional reminder for Clinical Visit #2)
Clinic Visit #2	Assessment for major and minor failure & assessment of pain and parent satisfaction	T = 3 months
Intermediate Contact	Attrition prevention, update contact information, follow-up on pain	T = 4.5 months (Additional call reminder for Clinical Visit #3)
Clinic Visit #3	Reapplication of SDF in that group; Assessment for major & minor failure, radiographs*, and assessment of pain and parent satisfaction	T = 6 months

Intermediate Contact	Attrition prevention, update contact information, follow-up on pain	T = 9 months (Additional call for scheduling/reminder for Clinical Visit #4)
Clinic Visit #4	Assessment for major & minor failure, radiographs*, and final questionnaires	T = 12 months

\* Radiographs will be obtained only if an existing radiograph within 30 days of the visit is not available.

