### **3.5. Silver Diamine Fluoride Variations in Application**

While much of the previously presented research suggests that there are potential positive effects of SDF, there are still many potential variations in regimens for application. Many would assume that for effective arrest of caries, it would be important for carious debris to be removed reducing the bacterial load. However, it has been shown that caries removal did not offer any significant beneficial effect in terms of arresting carious lesions and only showed a reduction in the number

of arrested lesions that turned black in the NaF group, as 100 percent of the lesions in the SDF group presented with a black coloration regardless of caries removal. For this reason, it has been suggested that caries removal would be unnecessary, which would make the procedure more simple and could increase the potential for patient acceptability which is important because it is one of the advantages of this product.

Many studies have shown a variation in number of applications and concentrations, leading to the research question of determining an exact regimen. In terms of concentration, when observed at 6 months, it was noted that a single application of 38 percent SDF could arrest caries in comparison to 12 percent SDF, which could not. Regarding the optimal number of applications, it was shown that an annual topical application of 38 percent SDF would arrest 37 percent of caries at 12 months and up to 79.2 percent of caries at 24 months, while biannual applications resulted in 53 percent arrested caries at 12 months and 90.7 percent arrested caries at 24 months.

Due to the potentially highly positive caries arrest effects of SDF, research has been conducted in an attempt to prevent washing away of the product when placed on the tooth surface. It has been postulated that if the treated surface was to turn instantaneously black, this would indicate that the process had been accelerated and was in turn more effective. Studies have shown that applications of 10% stannous fluoride or tannic acid were not shown to have an additional benefit in arresting caries although they may have appeared to accelerate the process of SDF uptake by the tooth surface.

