## 7. Study Outcomes

### 7.1. Questionnaires + Acceptability Measures

At the baseline clinical visit:

- *Pediatric Medical History Form*
  - Mott Children's Health Center/University of Michigan School of Dentistry Children's Clinic standard form
- *CRF 05 Baseline Parent Questionnaire* (Appendix 10, CRF 05)
- *CRF 06 Child Questionnaire* (Appendix 10, CRF 06)

When scheduled intermediate contact occurs via phone (or in person if presenting to MCHC/UMSOD for other reasons) at 1, 2, 4.5, and 9 months, the following form will be completed by the personnel making the contact, documenting the answers provided by the parent:

- *CRF 07 Intermediate Contact* (Appendix 10, CRF 07)

At recall visits (3 & 6 months, 12 month final recall, plus emergency visits) the parent and patient will complete:

- *CRF 08 Follow-up Parent Questionnaire* (Appendix 10, CRF 08)  
OR
- *CRF 09 6 & 12 Month Parent Questionnaire* (Appendix 10, CRF 09)
- *CRF 06 Child Questionnaire* (Appendix 10, CRF 06)

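### Withdrawing every child at first failure, with no later questionnaires, leaves earlier failures out of the month-12 acceptability data, unequally by arm, and the analysis plan has no rule for them

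*Combined protocol and SAP*

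**What the plan says.** Acceptability is one of the stated objectives (Section 2): "The perceptions of parents and patients to both treatment modalities and their levels of acceptability".

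Section 6 sets the rule at failure: "In the event of minor or major failure in either study group, the subject will be withdrawn from the study". The tooth is then counted as a failure and a treatment deviation form (CRF 04) is completed. Section 4.4 is worded differently. When treatment is failing, "the provider will recommend additional treatment and can withdraw the patient at any time", which leaves the decision open.

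Section 7.1 sets the timing of the questionnaires: "At recall visits (3 & 6 months, 12 month final recall, plus emergency visits) the parent and patient will complete" a parent form (CRF 08 or CRF 09) and the child form (CRF 06). Table 1 lists parent satisfaction at months 3 and 6 and the final questionnaires at month 12.

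Section 9 has the reason for withdrawal recorded, partly for what it shows about acceptance, and mentions additional forms and a disenrolment letter. Section 11 continues follow-up only for children who cannot complete an intermediate recall visit but wish to stay in.

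The analysis is one sentence in Section 10: "Chi-square tests will also be used to determine differences in dropout rates, failure rates, patient satisfaction/acceptance, and overall cost". It gives no time point for acceptability and no rule for withdrawn families.

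**The concern.** The clinical outcome survives withdrawal, because the tooth is still counted as a failure. The month-12 questionnaires have no such protection. Whether a family answers them depends on whether its treatment failed earlier. That is an event after randomisation, and the plan expects its frequency to differ between the arms.

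A chi-square test on month-12 answers would then compare two groups selected by outcome. If failed families are less satisfied, each arm looks better than it is, and the arm with more early failures gains more. A real difference in acceptability could be understated, hidden or, with unequal failure timing, reversed.

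**Working it through.** **Inputs from the documents**
- Conventional failure at one year (Section 4.2): "the combined failure rate for conventional restorative techniques (e.g. compomers) is approximately 29% at one year follow-up".
- SDF failure at one year, the planning value (Section 4.2): "while application of silver diamine fluoride has a failure rate of 63% at one year follow-up".
- SDF failure with biannual application: Section 5.2 schedules a second application at 6 months, and Section 3.5 reports that "biannual applications resulted in 53 percent arrested caries at 12 months". This gives 100 - 53 = 47%.
- Enrolment: 98 children allocated 1:1, so 49 per arm.

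**The plan's own figure.** A two-sided 5% test of 29% against 63% with 80% power (pooled variance, no continuity correction) needs 33 per arm, against the stated 34. Inflating for 30% attrition, 34/0.70 = 48.6, rounded up to 49 per arm or 98 in total, as stated. The sample size is not in dispute here.

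**Assumptions not in the documents**
- f, the share of failures found before the month-12 visit: 50%, 75% or 100%, equal in both arms.
- Satisfaction: 90% after success and 40% after failure.
- No other dropout.

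**Formulas**, with failure probability p:
- Families answering at month 12 = 49 × (1 - p·f)
- Share of them with success = (1 - p)/(1 - p·f)
- True satisfaction = 0.9(1 - p) + 0.4p
- Observed satisfaction = [0.9(1 - p) + 0.4p(1 - f)]/(1 - p·f)

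**True rates**
- SDF at 63%: 0.9 × 0.37 + 0.4 × 0.63 = 58.5%
- SDF at 47%: 0.9 × 0.53 + 0.4 × 0.47 = 66.5%
- Conventional at 29%: 0.9 × 0.71 + 0.4 × 0.29 = 75.5%
- True differences: -17.0 points (63%) and -9.0 points (47%)

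**Month-12 data under the withdrawal rule**

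| Arm | Quantity | f = 50% | f = 75% | f = 100% |
|---|---|---|---|---|
| SDF, 63% | answering (of 49) | 33.6 | 25.8 | 18.1 |
| | share with success | 54% | 70% | 100% |
| | observed satisfied | 67.0% | 75.1% | 90% |
| SDF, 47% | answering (of 49) | 37.5 | 31.7 | 26.0 |
| | share with success | 69% | 82% | 100% |
| | observed satisfied | 74.6% | 80.9% | 90% |
| Conventional, 29% | answering (of 49) | 41.9 | 38.3 | 34.8 |
| | share with success | 83% | 91% | 100% |
| | observed satisfied | 81.5% | 85.4% | 90% |
| Difference, SDF at 63% | true -17.0 | -14.5 | -10.3 | 0 |
| Difference, SDF at 47% | true -9.0 | -6.9 | -4.4 | 0 |

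**Sensitivity to the assumptions**
- *Timing from a constant hazard.* The share of failures found by the 6-month visit is (1 - √(1 - p))/p, which is 62% for p = 0.63 and 54% for p = 0.29. The observed rates are then 70.4% and 82.1%, a difference of about -12 points.
- *Unequal timing.* If all SDF failures (at 63%) but only half the conventional failures come early, the data show 90% against 81.5%. The sign is reversed.
- *Late failures.* If only one third of failures are found early, successes make up 0.37/0.79 = 47% of SDF respondents at 63% failure.
- *No link.* If satisfaction does not depend on failure, observed and true rates agree whatever f is.

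**The case against.** The strongest reply is that Section 10 names no time point, so a month-12 comparison among those still in the study is only one reading. Forms are also completed at months 3 and 6 and at emergency visits. These are the visits where failures are found, so many failed families will have an answer from that visit. Section 9 records reasons for withdrawal, and the content of its additional forms cannot be judged because the CRFs are not in the text.

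This stands in part. A reader might infer that the whole acceptability objective loses its randomised comparison. The documents do not support that: the month-3 data are largely intact. But Section 10 does not say that failure-visit answers will be used, and a recorded reason does not replace a satisfaction score. At month 3 or an emergency visit the parent form may also be CRF 08, since CRF 09 is titled for months 6 and 12.

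A second reply concerns direction. An SDF minor failure can be soft dentin alone, possibly without symptoms, and a large fall in satisfaction is then speculative. Section 3.4 names black staining as the most notable drawback. It also affects arrested lesions, and those families stay in. This stands. A reader might infer that the plan must conceal dissatisfaction with SDF, or that month-12 answers come mainly from successes. Both depend on failure timing and on a link between failure and dissatisfaction, which the documents do not give. Failures first found at month 12 still contribute.

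A third reply is that a month-12 answer from a re-treated family partly rates the re-treatment. This is correct, and it shapes the analysis rule below.

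**Conclusion.** The concern holds for the month-12 acceptability data. As written, families whose treatment failed earlier are absent from those data. With similar failure timing in the two arms, more are absent from the SDF arm, at either 63% or 47% failure against 29%. A month-12 chi-square test would therefore not compare the randomised groups, and the plan has no rule for bringing in the answers it does collect from failed families.

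Under the 90%/40% assumption, with 50% to 75% of failures found early and equally timed, the distortion is about 2.5 to 7 points at 63% SDF failure and about 2 to 5 points at 47%. The difference vanishes only if every failure precedes month 12. Size and direction remain conditional on timing and on the failure-satisfaction link. The primary clinical outcome and the sample size are not affected. This is a secondary objective, but the gap should be closed because doing so is cheap.

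**What to change.** - **Sections 4.4 and 6:** reconcile the discretionary and mandatory withdrawal wording.
- **Sections 6 and 7.1:** separate stopping study treatment from stopping questionnaires. Complete CRF 09 and CRF 06 at the failure or withdrawal visit. Offer the parent the CRF 09 questions by phone at month 12 unless the family refuses. Clinical care is unchanged.
- **Section 10:** name the time point and compare acceptability in all randomised children. For failed families, use the failure- or withdrawal-visit answer as the rating of the assigned treatment. Use their month-12 answer, which includes experience of re-treatment, as a sensitivity analysis. Label any comparison restricted to non-failures as descriptive.

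The cost is one extra phone contact per failed or withdrawn family, using existing forms, and a short change to the protocol and consent wording.
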